The study treatment is non-fat cow's milk powder or placebo ingested in a baked form. The non-fat cow's milk powder will be provided by the University of North Carolina (UNC). It is manufactured by The Milky Whey, Inc & TMW International. It will be refrigerated at the site at 2 through 8°C until provided to the participants. Detailed instructions will be provided regarding how the baking should be performed.

The doses chosen are based on prior milk OIT studies, which have all used unheated milk. We anticipate similar efficacy with greater safety using this approach.

b. Justification and safety information if FDA approved drugs will be administered for nonFDA approved indications or if doses or routes of administration or participant populations are changed.

Aside from the skin testing extracts, this study will not use any drugs, but rather foods commonly available in households, prepared using a standard oven. Most milk OIT studies to date have used unheated milk at maintenance doses ranging from 500- 4000 mg. As described in the background section, these have shown high rates of adverse reactions, ranging from mild, local symptoms, such as oral itching, to systemic allergic reactions.

Baking milk has been shown to modify the allergen and make it less allergenic and therefore less likely to induce adverse reactions. It has been shown that 50-75% of children with

CMA tolerate baked milk at full servings, such as a cupcake or muffin, and many are already incorporating these foods into their diet at home.¹³ However, the remaining 25-50% of children with CMA are not able to tolerate baked milk at standard doses. Our dosing regimen will start with extremely small doses of baked milk protein and gradual escalation.

We believe that the chemistry and manufacturing of the non-fat milk powder and Tapioca Flour does not present signals of potential human risk, beyond the inherent risk associated with the investigational treatment protocol. This milk powder has been approved by the Food & Drug administration for use in other clinical trials (IND: 77,468) and in our study (IND: 17114).

c. Justification and safety information if non-FDA approved drugs without an IND will be administered.

N/A

7. Study Statistics

a. Primary outcome variable.

The primary objective of this trial is to study the safety of baked milk OIT, defined as the incidence of adverse events on baked milk OIT compared to adverse events on placebo.

b. Secondary outcome variables.

As mentioned previously, there has only been 1 prior study using baked milk OIT. Goldberg et al had a different primary outcome which was the goal of attaining a maintenance BM dose of 1.3g/day.²⁸ Only 21% reached that goal but as mentioned above, the study protocol was different than our study protocol.

Based on these prior studies, we would expect that at most 10% of subjects in the placebo arm and at least 60% of subjects in the treatment arm would tolerate 2 grams of unheated milk at the 1 year OFC. To achieve an alpha of 0.05 and a power of 0.8, 14 subjects are needed in each group. 15 participants per group would allow for a 7% drop out rate.

Statistical plan:

We will display summary statistics for each variable to keep track of missing data, and to be alerted to suspicious patterns in the data and outliers. We will initially focus on the primary aim of the study. We will examine adverse event endpoints to estimate 1) the risk associated with OIT and 2) compare the risks of OIT between the risks of adverse reactions in the placebo group. We will tabulate the total number of serious adverse events (SAE) for the active treatment study population and construct a 95% confidence interval for this total number of adverse events. We will also calculate the proportion of subjects who experienced an SAE along with the 95% CI. We will calculate the proportion of subjects who experienced an SAE and construct the 95% CI. We will compare the proportion of doses resulting in an SAE between groups using Fisher's exact test. We will compare the number of adverse events between groups using the Kruskall-Wallis test if the variances between the groups are similar.

In addition to efficacy endpoints, we will tabulate data and calculate the proportion of subjects who achieved a clinical response and construct 95% confidence intervals. We will do this for each time point being evaluated so that we have estimates of clinical response rates after completion of 1 year of OIT, after 2 years of OIT, and after 1 year of placebo.

We will also compare clinical response rates between the active treatment and placebo groups at the year 1 and year 2 OFCs. We will tabulate the clinical response rates by group for each time point and use a t-test for difference in proportions to test for statistical significances in response rates between groups.

We will also compare change in maximum tolerated dose of baked milk from baseline to end of year 1 and end of year 2. We will compare each subject's maximum tolerated dose of baked milk compared to maximum tolerated dose of unheated milk at the end of year 2. We will use a t-test for to test for statistical significances in change in amount tolerated between groups.

Summary descriptive statistics for baseline and demographic characteristics and biomarker and mechanistic studies will be provided for all enrolled participants. Demographic data will include age, race, sex, body weight, and height. Biomarker and mechanistic data will include cow's milk IgE and IgG4, goat and sheep milk IgE, and lymphocyte analysis. These data will be presented in the following manner:

- Continuous data (i.e., age, body weight, and height) will be summarized descriptively by mean, standard deviation, median, and range.
- Categorical data will be presented as enumerations and percentages.

Statistical presentation for baseline and demographic characteristics may be further summarized as appropriate.

d. Early stopping rules.

Study enrollment and treatment will be suspended pending expedited review of all pertinent data by the IRB and the DSMB if the following occur:

- Any death.
- More than one severe anaphylactic reaction related to baked milk immunotherapy dosing at any stage of the protocol.
- More than three subjects require more than one injection of epinephrine during dosing of the baked milk immunotherapy.
- The first 5 subjects cannot reach 3 mg of OIT.

Additionally, the study will be stopped upon enrollment and completion of the defined number of participants that meet the selection criteria.

8. Risks

a. Medical risks, listing all procedures, their major and minor risks and expected frequency.

i. Baked Milk Powder administered via the oral route

The escalation day followed by the build-up phase of immunotherapy is based on previous experience with peanut, egg, wheat, and unheated milk OIT. In the Principal Investigator's experience, the initial doses have been well tolerated. Therefore, the initial dose escalation day was included to shorten the prolonged build-up phase. The likelihood of participants experiencing allergic symptoms will be decreased by the OIT protocol, starting at extremely small amounts with gradual escalation.

Unheated oral immunotherapy has shown a high rate of adverse reactions. In 2011, Martorell et al conducted a 1 year milk OIT study in 2-3 year old children. While 90% were desensitized, 47% developed moderate reactions (rhinoconjunctivitis, wheezing, vomiting, urticaria) over the course of treatment.¹⁹ In 2012, we examined the safety and efficacy of OIT and SLIT (sublingual immunotherapy) for cow's milk allergy. The study reported the reaction rate during the initial OIT escalation (36%), 1000 mg OIT escalation and maintenance (30%), and 2000 mg OIT escalation and maintenance (27%).¹⁸ The majority of symptoms were mild and localized to oral pruritus.¹⁸ During this study, antihistamines were used in 11% of doses during initial OIT escalation, 3.5% of doses in the 1000 mg escalation and maintenance, and 11% of doses in the 2000 mg OIT escalation and maintenance. A β -agonist was required in 1.5%, 2%, and 1.5% of doses in each respective group. Epinephrine was used for 4 OIT doses.¹⁸ In addition, 10-20% of subjects have dropped out of OIT trials due to adverse reactions, most commonly chronic abdominal pain.^{12,26}

We would view these risks as worst case scenario, since we expect far fewer adverse reaction with the heat modified milk proteins.

ii. Allergy Skin Testing

There is a risk of minor discomfort and itching and a transient hive. A localized wheal and flare will occur at the site of the histamine control. A similar reaction may occur at the site of milk extract. Fewer than 5 in 10,000 tests results in a systemic reaction (e.g. sneezing, runny nose, itchy eyes, or hives), and, even more rarely, systemic reactions that can be life-threatening.²⁹⁻³² There have been no systemic reactions in the principal investigator's experience with over 75,000 skin tests.

iii. Blood Collection

There is a risk of minor discomfort or bruising at the site of the blood draw. Some people may experience lightheadedness. Very rarely, an infection can develop at the site of the venipuncture.

iv. Spirometry and Peak Flow

The minor risk is of slight discomfort associated with forceful expiration and, occasionally, lightheadedness.

v. Oral food challenge

In this study, children will undergo oral food challenges to determine baseline level of reactivity and response to therapy. The risk attendant to an oral food challenge is the same as those that may occur from a food-allergy reaction and are typically short-lived (less than 2 hours). Common symptoms may include urticaria, angioedema, nausea, abdominal discomfort, vomiting and/or diarrhea, rhinorrhea, sneezing and/or mild wheezing. The major risks involved include severe breathing difficulties, and rarely, a drop in blood pressure. A severe outcome is theoretically possible and one death has occurred in a medically supervised oral food challenge. However, to date the primary investigators have performed more than 5000 oral food challenges without a serious life-threatening anaphylactic reaction or need for hospitalization.

We have chosen to only challenge to baked milk at screening and at the end of year 1 in an effort to reduce risk, recognizing that all subjects who react to heated milk would react to unheated milk at the same or lower dose.

- vi. Medical Exams: There are no known risks for the physical exam.
- vii. Pregnancy Tests: There is a risk of loss of confidentiality of results as positive tests would be provided to the parents in all participants <18 years old.

b. Steps taken to minimize the risks.

i. Baked Milk Powder administered via the oral route

The use of heated milk in this study is specifically designed to minimize the risk of treatment. In addition, as with our studies using unheated milk, the initial doses are extremely small and subsequent dose increases will be gradual. Dose escalation will be done under direct supervision of a physician. Appropriate medications, equipment, and personnel will be available in case of a severe reaction, especially given that the study will be conducted in the PCRU on Bloomberg 9. Upon completion of a food challenge or IDE, all participants will be observed for at least 2 hours, unless the OFC is unblinded and the participant had a negative challenge to placebo. For any severe systemic reaction, all subjects will be observed for at least 4 hours or until signs of clinical reactivity subside. Any subject with ongoing severe systemic symptoms (i.e. persistent vomiting, wheeze, cough, FEV1<80% baseline level, hypotension, or laryngeal edema manifested by difficulty breathing or speaking) will be observed in clinic until symptoms resolve. If they do not resolve, the subject will be hospitalized. In the event of a negative challenge to placebo, participants can be sent home after unblinding.

For the build-up visits, subjects will be observed for at least 1 hour after dosing. For any moderate symptoms, all participants will be observed for at least 2 hours. For any severe systemic reaction, all subjects will be observed for at least 4 hours or until signs of clinical reactivity subside.

All subjects will have injectable epinephrine (available at all times, and clear instructions about its use. The subject will be contacted on the day after dose escalation to monitor for adverse events. A 24-hour physician emergency number will be given to the subject.

ii. Allergy Skin Testing

SPT will be performed by a trained physician or nurse. Appropriate medications will be available at the time of testing (antihistamine, steroids, short-acting beta agonist, and epinephrine). A designated physician will be immediately available to provide medical assistance if necessary. Any participant with an asthma exacerbation at the time of the visit will not undergo skin testing. He/she may return at a later date when his/her asthma is under control. An asthma exacerbation will be defined as wheezing on chest auscultation, currently taking oral corticosteroids, or having FEV1 or PEFR <70% predicted.

iii. Blood Collection

A staff member who is trained to draw blood from children will collect the samples. We will not draw more than 3 cc/kg/month/subject of blood.

iv. Spirometry and Peak Flow

Spirometry and peak flow readings will be performed by trained personnel. v.

Oral food challenge

Trained staff will be present to administer study food challenges and a physician will be at the bedside to provide oversight, evaluation, and treatment as needed. The risks of oral food challenges are minimized by the following procedures:

- Children must have a stable baseline examination prior to undergoing the challenge without significant symptoms of flaring atopic dermatitis, exacerbations of rhinorrhea, current urticarial, or other symptoms evaluated during food challenges
- Children must have no wheezing or repetitive cough prior to challenge
- Children must have no current illnesses (e.g. fever) at time of oral challenge
- Medications (epinephrine, intravenous fluids, antihistamines, ranitidine, vasopressors, beta-agonists, and steroids), personnel and equipment (oxygen,

resuscitation equipment) will be immediately available to treat allergic reactions should they occur.

- Children will have discontinued antihistamines and bronchodilators for appropriate periods prior to challenge, thereby allowing investigators to perform challenges only when participants are stable without influence of medications.
- The food will be provided gradually, at 15 minute intervals, beginning with a dose unlikely to trigger a reaction and progress stepwise with escalating doses.
- Vital signs (heart rate, blood pressure, respiratory rate) and physical examination will be undertaken at baseline and at the end of the OFC with a focused examination undertaken prior to each dose
- Challenges will be stopped, and medications administered, in the event of any objective symptoms.

All participants will be observed for at least 2 hours, unless the OFC is unblinded and the participant had a negative challenge to placebo. For any severe systemic reaction, all subjects will be observed for at least 4 hours or until signs of clinical reactivity subside.

vi. Pregnancy Tests:

Personal identifiers will not be placed on collected data.

c. Plan for reporting unanticipated problems or study deviations.

Reporting will occur as follows:

- i. Toxicity will be graded according to the NCI-CTC for application in adverse event reporting. The NCI-CTC has been reviewed specifically for this protocol and is appropriate for this study population. The purpose of using the NCI-CTC system is to provide standard language to describe toxicities, and to facilitate tabulation and analysis of the data and assessment of the clinical significance of treatment-related toxicities. The investigator will try to determine the relationship of toxicity to baked milk immunotherapy as not related, possibly related, or definitely related using standard criteria for clinical trials. All grades of toxicity will be noted. Toxicity grades are assigned by the study site to indicate the severity of adverse experiences and toxicities.
- ii. Adverse events, not included in the NCI-CTC listing, should be recorded and graded 0-4 according to the General Grade Definition provided below:

Table 7: General Grade Definitions

| Grade 0 | Mild | Transient or mild discomforts (< 48 hours), no or |
|---------|-----------------|--|
| | | minimal medical intervention/therapy required, |
| | | hospitalization not necessary (non-prescription or single- |
| | | use prescription therapy may be employed to relieve |
| | | symptoms, e.g., aspirin for simple headache, |
| | | acetaminophen for postsurgical pain) |
| Grade 1 | Moderate | Mild to moderate limitation in activity, some assistance |
| | | may be needed; no or minimal intervention/therapy |
| | | required, hospitalization possible. |
| Grade 2 | Severe | Marked limitation in activity, some assistance usually |
| | | required; medical intervention/therapy required |
| | | hospitalization possible. |
| Grade 3 | Lifethreatening | Extreme limitation in activity, significant assistance |
| | | required; significant medical/therapy intervention |
| | | required hospitalization or hospice care probable. |
| Grade 4 | Death | Death |

iii. Adverse Event Reporting:

Within the context of this study, blood draws, allergy skin prick tests, dose increases and oral food allergy challenge tests will be observed and recorded. Adverse events (AEs) that are temporally related to these procedures or to home dosing with the study medications (during 3 days following the procedure) will be reportable adverse events. Anticipated local reactions to prick skin tests and oral food challenges reactions occurring during the challenge procedure will not be additionally reported on an adverse event form unless the reaction results in a serious adverse event. In that case it will be reported both on the reaction form and on a serious adverse event form.

The following events would be considered expected events for the procedures being performed:

- Blood draw: nausea and vomiting, local infection, and fainting
- Prick skin test: Pruritus, transient hive, systemic allergic reaction
- Oral food challenges and dosing with study medications: allergic reactions related to the skin (hives, pruritus, eczema flare), the respiratory tract (nasal congestion, rhinorrhea, fits of sneezing, difficulty breathing, asthma), and the GI tract (oropharyngeal pruritus and edema, nausea, vomiting and diarrhea).

All "unanticipated" adverse events related to the experimental procedures will be reported to the DSMB in an expedited manner if they are Grade 2 and above in severity. All "anticipated" adverse events related to the experimental procedures will also be reported in an expedited manner if they are Grade 2 and above in severity. Subject deaths are reportable within 24 hours. The investigator will continue to follow or obtain documentation of the resolution course of such an event. A copy of the annual report of adverse events will be reported to the IRB.

iv. Data and Safety Monitoring:

A Data Safety Monitoring Board will be convened for overview of this study. The Principal Investigator and Co-Investigators are responsible for collecting and recoding all clinical data. As these results are collected, all toxicities and adverse events will be identified and reported to the PI. Adverse events will be reported as described above. The Principal Investigator will determine the relationship of the event to the study intervention and decide the course of action for the study participant.

Yearly reports will be made to the DSMB and proper Institutional Committees, as required. All adverse events will be kept in a computerized file by numerical identifier.

In the event that the study is stopped because of adverse event(s), it will not be resumed until information regarding the adverse event(s) has been discussed with the DSMB and the DSMB concurs with resumption of the studies.

d. Legal risks such as the risks that would be associated with breach of confidentiality.

The risk of breach of confidentiality will be minimized by using unique identifiers for participants and keeping the record that links the identifier to the participant in a locked file cabinet accessible only to the investigators.

Genomic research and broad sharing of genomic data will have an "opt-in" and "opt-out" area on the consent and will not affect the participants' eligibility to take part in the study. In addition, personal identifying information about the subject (such as name, phone number, address) will NOT be included in these genomic databases or shared with others, including our collaborator, La Jolla Institute.

e. Financial risks to the participants.

The study does not provide routine care or any medications or treatments for general health or allergic problems (although we will be available for phone consultation regarding possible reactions). All costs associated with study visits, skin testing, spirometry, blood drawing, food challenges, and OIT protein are covered by the investigators. All participants will be required to provide a muffin/cupcake mix in which they can bake the weekly doses of OIT. This will be provided by the family so that flavor/variety can be altered for each child's preference. All participants will be required to have an epinephrine auto-injector available at

home during immunotherapy treatment. If they do not already have one, they will be responsible for the cost of this medication.

9. Benefits

a. Description of the probable benefits for the participant and for society.

The benefits for the participant include the possibility of a change in sensitivity to milk and decreased allergic reactions following an accidental ingestion of milk. Another possible benefit is the possibility of altering the natural course of the milk allergy.

The potential benefit to the subject and family is that this active protocol may induce tolerance to milk protein in someone that is unlikely to naturally "outgrown" his/her allergy. If tolerance is achieved, this then make impact quality of life.

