1. OFC: The initial and year 1 and 2 food challenges will be double-blind placebo-controlled food challenges (DBPCFC) in which both the patient and clinician will be blinded. The DBPCFC will be done in accordance with standard procedures. All oral food challenges will be performed in the PCRU with direct physician supervision, emergency medications immediately available, and in accordance with standard procedures. We will prepare challenge materials using our standard operating procedures (SOP). The initial DBPCFC will be a challenge to baked milk or placebo. Milk will be administered in the form of non-fat milk powder (provided by the University of North Carolina (UNC), manufactured by The Milky Whey, Inc & TMW International), added to a cake and baked at 350°F/180°C (at least) for at least 30 minutes. The first DBPCFC will consist of a maximum cumulative dose of 444 mg of baked milk powder in gradually increasing doses at 15 minute intervals. The doses will be prepared by the research nutrition staff and distributed as listed in table 2 below. Frequent assessments are made for symptoms affecting the skin, gastrointestinal tract, cardiovascular system, and/or respiratory tract. Objective symptoms indicate a positive reaction at which time dosing is terminated and appropriate treatment is administered.

Table 2. Baseline Food Challenge (Baked Milk) DBPCFC #1:

| Dose # | Dose (mg) of milk protein | Cumulative Dose (mg)(mg) |
|--------|---------------------------|--------------------------|
| 1 | 1 mg | 1 mg |
| 2 | 3 mg | 4 mg |
| 3 | 10 mg | 14 mg |
| 4 | 30 mg | 44mg |
| 5 | 100 mg | 144 mg |
| 6 | 300 mg | 444 mg |

At the end of year 1, participants will undergo DBPCFC#2 to up to maximum cumulative dose of 4044 mg of baked milk. The doses will be prepared by the research nutrition staff and distributed as listed in table 3. The subject will return within 21 days for the second half of the challenge.

| Dose # | Dose (mg) of milk protein | Cumulative Dose (mg) |
|--------|---------------------------|----------------------|
| 1 | 1 mg | 1 mg |
| 2 | 3 mg | 4 mg |
| 3 | 10 mg | 14 mg |
| 4 | 30 mg | 44mg |
| 5 | 100 mg | 144 mg |
| 6 | 300 mg | 444 mg |
| 7 | 600 mg | 1044 mg |
| 8 | 1000 mg | 2044 mg |
| 9 | 2000 mg | 4044 mg |

Table 3. End of Year 1 Food Challenge (Baked Milk) DBPCFC #2:

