At the end of year 2, participants will undergo DBPCFC #3 to up to maximum cumulative dose of 4044 mg of baked milk. During year 2, all participants will be on active OIT and are required to reach at least 750 mg of baked milk protein at least 8 weeks prior to the end of year 3. Therefore, DBPCFC#3 will start at 444 mg. The doses will be prepared by the research nutrition staff and distributed as listed in table 4.

Table 4. End of Year 2 Food Challenge (Baked Milk) DBPCFC #3:

| Dose # | Dose (mg) of milk protein | Cumulative Dose (mg) |
|--------|---------------------------|----------------------|
| 1 | 444 mg | 444 mg |
| 2 | 600 mg | 1044 mg |
| 3 | 1000 mg | 2044 mg |
| 4 | 2000 mg | 4044 mg |

Subjects who tolerate at least 2000 mg of baked milk the DBPCFC#3 will return within 2 weeks to undergo DBPCFC#4 to up to 8030 mg of unheated milk in the form of non-fat milk powder or placebo in a blinded vehicle. The study nutritionist will create these doses based on the schedule in Table 5.

| Dose # | Dose (mg) of milk protein | Cumulative Dose (mg) |
|--------|---------------------------|----------------------|
| 1 | 30 | 30 |
| 2 | 100 | 130 |
| 3 | 300 | 430 |
| 4 | 600 | 1030 |
| 5 | 1000 | 2030 |
| 6 | 1500 | 3530 |
| 7 | 2000 | 5530 |
| 8 | 2500 | 8030 |

Table 5. Year 2 Food Challenge (Unheated Milk) DBPCFC #4:

These challenges will be very helpful to determine the dose of milk that should be safe to incorporate into the diet. All participants will be provided specific guidelines as to the amount of heated and unheated milk that can be introduced into their diets at study completion.

- 2. Skin prick tests: A skin prick test using cow's milk extract will be performed using standard procedures. The patient must be off antihistamines for 5 days for long acting and 3 days for short acting prior to skin testing. A skin test probe (Greer Pick) is pressed through a commercial milk extract (Greer Laboratories) into the epidermis. Histamine (positive) and saline-glycerin (negative) controls are placed to establish that the response is not blocked and to determine if there is dermatographism, respectively. A study physician will be available to monitor for any adverse events.

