each visit as well. Maintenance visits may occur via phone, video visit, or in-person at the discretion of the PI.

F. Double Blind Placebo Control Food Challenge #2:

At week 52, after at least 8 weeks of OIT maintenance therapy, study participants will undergo DBPCFC #2. Participants will be asked to fill out a gastrointestinal assessment and quality of life questionnaire prior to DBPCFC #2. A limited physical exam, urine pregnancy (if indicated), and peak flow rate will be conducted. Blood will be collected and skin testing will be repeated. If the exam is normal, urine pregnancy test is negative, and PFR \geq 80% predicted, the study participants will undergo an oral food challenge with a cumulative dose of 4044 mg of baked milk or placebo as shown above in Table 3. Participants will receive doses every 15 minutes and will be monitored for symptoms of allergic reaction. The second half of the DBPCFC will occur within 21 days.

G. Unblinded Phase:

Unblinding will occur after DBPCFC #2.

1. Build-up Phase Post 1 Year OFC for Placebo-Treated Subjects:

The placebo group will be offered the option of crossing over into active therapy with dose escalation to a maximum of 2000 mg maintenance. They will follow the same protocol as the initial active treatment group. Blood will be collected at the start of maintenance.

2. Build-up Phase Post 1 Year OFC for those in Initial Active Treatment Group

Those in the initial active treatment group who were unable to reach the goal maintenance dose of 2000 mg by study week 44, will resume dose build-up until they reach a maximum of 2000 mg/day if tolerated. They will resume the same initial protocol. If the patient does not tolerate three consecutive escalation attempts, then they will remain at their current dose for the remainder of the study period.

3. Maintenance Phase Post 1 Year OFC:

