At the end of study year 2 (week 106), study participants will undergo DBPCFC #3 to baked milk with dosing as listed above in Table 4. Participants will be asked to fill out a gastrointestinal assessment and quality of life questionnaire prior to DBPCFC #3. A limited physical exam, urine pregnancy test (if indicated) and peak flow rate will be conducted. Blood will be collected and skin testing will be repeated. If the exam is normal, urine pregnancy test is negative, and PFR \geq 80% of normal, the study participants will undergo an oral food challenge with a cumulative dose of 4044 mg of either baked milk or placebo in a blinded manner. Participants will receive doses every 15 minutes and will be monitored for symptoms of allergic reaction. The second half of the DBPCFC will occur within 21 days. If no symptoms occur during the first half of DBPCFC#3, then the second half of the challenge could occur on the same day at the discretion of the principal investigator.

5. Study Year 2 OFC to Unheated Milk (DBPCFC #4)

Within two weeks of the completion of DBPCFC #3, study participants who tolerated at least 2000 mg of baked milk during DBPCFC #3 will undergo DBPCFC#4 with a cumulative of 8030 mg of unheated milk powder or placebo in a blinded manner with dosing as listed in table 5. A limited physical exam, urine pregnancy and peak flow rate will be conducted. If the exam is normal, urine pregnancy test is negative, and PFR \geq 80% of normal, the study participants will undergo an oral food challenge to unheated milk powder or placebo. The second half of the DBPCFC will occur within 21 days. If no symptoms occur during the first half of DBPCFC#4, then the second half of the challenge could occur on the same day at the discretion of the principal investigator.

H. Follow-up Period:

- 1. Subjects who discontinue study treatment before the end of the study will complete an Early Discontinuation Visit 1-2 weeks after their last dose of study treatment. During that visit, they will have a physical exam and urine pregnancy test (if applicable). Daily diaries and interval history will be reviewed. Subjects who complete DBPCFC#2 and then leave the study early will be asked to sign a consent to participate in follow-up (as detailed below in #4) if they have been given instructions to introduce milk at home.

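### The sample size of 14 per group is justified by tolerance of 2 g unheated milk at 1 year, placebo versus active, which no challenge in the trial measures

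*Combined protocol and SAP*

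**What the plan says.** Section 7c contains the only sample-size justification. It expects at most 10% of placebo subjects to respond and that "at least 60% of subjects in the treatment arm would tolerate 2 grams of unheated milk at the 1 year OFC". With alpha 0.05 and power 0.8 this leads to 14 per group, raised to 15 to allow for 7% dropout.

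The challenges are described differently everywhere else:

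- **Year 1 (DBPCFC #2) is baked milk.** Section 4, item 1: "At the end of year 1, participants will undergo DBPCFC#2 to up to maximum cumulative dose of 4044 mg of baked milk". Section 4F has participants "undergo an oral food challenge with a cumulative dose of 4044 mg of baked milk or placebo as shown above in Table 3". Table 8 lists no other challenge at weeks 52 and 54.
- **This is deliberate.** Section 8a.v: "We have chosen to only challenge to baked milk at screening and at the end of year 1", to reduce risk, "recognizing that all subjects who react to heated milk would react to unheated milk at the same or lower dose".
- **Unheated milk is given only in DBPCFC #4, after year 2, and only to some.** Section 4G.5: "study participants who tolerated at least 2000 mg of baked milk during DBPCFC #3 will undergo DBPCFC#4".
- **The placebo control ends at year 1.** Section 4G: "Unblinding will occur after DBPCFC #2". The placebo group is then offered active OIT, and section 4, item 1 describes everyone as on active OIT during year 2.

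Sections 2 and 7c define clinical response as tolerating 4 g of baked milk protein at 12 and 24 months, and 2 g of unheated milk at the end of year 2. Section 7c plans to compare response rates between active and placebo groups at both the year-1 and year-2 challenges, using a t-test.

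**The concern.** The sizing statement joins a food and dose (2 g unheated) with a time point (1 year) that the schedule never combines. Each exists separately; the combination does not. Changing one word does not repair it. If unheated is read as baked, the dose still differs from the 4 g responder definition. If 1 year is read as 2 years, there is no longer a placebo arm to which the 10% could apply.

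A reader would naturally credit the planned year-1 and year-2 responder tests with 80% power. Neither has stated rates or power, and the year-2 test is not placebo-controlled.

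**Working it through.** **1. Reproducing the plan's figure.** Inputs from section 7c: p0 = 0.10, p1 = 0.60, alpha = 0.05 (taken as two-sided, since sidedness is not stated), power 0.80, equal groups. With mean rate 0.35 and pooled variance under the null:

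n = [1.960·√(2·0.35·0.65) + 0.842·√(0.10·0.90 + 0.60·0.40)]² / (0.60 − 0.10)²
= (1.322 + 0.483)² / 0.25 = 13.04, so 14 per group.

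Dropout: 1 − 14/15 = 6.7%, which agrees with the stated 7%. The calculation is sound for its inputs; the endpoint is the problem.

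**2. Can 10% and 60% be carried over to 4 g baked milk at year 1?** Not without new argument.

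- By the premise in section 8a.v, anyone who tolerates a given dose of unheated milk also tolerates that dose baked. At 2 g, the baked rate is therefore at least the unheated rate in both arms. A ceiling of 10% for placebo is then no longer a ceiling, while a floor of 60% for active remains a floor.
- The responder dose is 4 g, not 2 g. Tolerating 4 g is harder, so the 60% floor no longer follows either.
- Every enrolled child must react at 444 mg or less of baked milk (section 5), which makes a low placebo rate plausible.
- The only prior baked-milk OIT rate cited is 3/14 = 21% (sections 3 and 7c), for reaching 1.3 g/day under a different protocol.

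**3. Power for the comparison that will be made.** All rates below are assumptions. I took the planned t-test literally: an equal-variance t-test on 0/1 outcomes, two-sided 0.05, with 2n − 2 degrees of freedom. Exact power is the sum, over all pairs (x active, y placebo responders) that reject, of Bin(x; n, p1)·Bin(y; n, p0).

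| Placebo rate | n per arm | Active 60% | Active 50% | Active 40% | Active rate for 80% power |
|---|---|---|---|---|---|
| 10% | 15 | 0.88 | 0.73 | 0.51 | 54% |
| 10% | 14 | 0.85 | 0.69 | 0.47 | 57% |
| 5% | 15 | 0.96 | 0.87 | 0.70 | 45% |
| 5% | 14 | 0.94 | 0.84 | 0.65 | 48% |
| 0% | 15 | >0.99 | 0.98 | 0.91 | 34% |
| 0% | 14 | >0.99 | 0.97 | 0.88 | 36% |

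For scale only, an active rate of 3/14 with 15 per arm gives 0.12, 0.22 and about 0.4 for placebo rates of 10%, 5% and 0%.

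**4. Year 2, 2 g unheated milk.** This compares about 2 years with about 1 year of active OIT. The documents give no rate for the crossover group, so power cannot be derived from them. As an illustration, take the original active group at 60%, 15 per group, every placebo child crossing over and no dropout:

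| Assumed crossover-group rate | 50% | 40% | 30% | 20% | 10% |
|---|---|---|---|---|---|
| Power | 0.08 | 0.18 | 0.37 | 0.63 | 0.88 |

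Only a crossover group that does about as badly as untreated placebo would recover the stated power.

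**The case against.** The strongest reply is that little depends on the paragraph. The primary outcome is safety, and the protocol introduces the efficacy outcomes as exploration. If 10% and 60% also held for baked milk at year 1, power would be 0.85 with 14 per arm and 0.88 with 15. These children react at 444 mg or less and are described as very unlikely to outgrow the allergy, so a placebo rate near zero at 4 g is credible and power would then be high. All of that stands, and it is why the point does not call for a larger trial. It does not make the justification correct: the same section calls clinical response the main secondary outcome and plans to test it between arms.

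Second, the protocol claims no power for year 2 and already lists a duration comparison and a separate crossover-group proportion. That is fair. But section 7c still describes the year-2 test as active versus placebo, so a plain statement is needed.

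Third, the power figures depend on method and on the number evaluable. Fisher's exact test at 10% versus 60% gives 0.74 with either 14 or 15 per arm, and 14 rather than 15 is the evaluable number the protocol plans for. This too stands, so the test and the number should be stated with any revised figure. The 21% is a different outcome under a different protocol and carries little weight beyond scale.

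**Conclusion.** The concern holds. The 14 per group and 80% power are computed correctly for a contrast the trial does not observe. The year-1 placebo-controlled responder comparison has no stated rates or power, and the year-2 unheated-milk comparison is neither placebo-controlled nor covered. Over assumed placebo rates of 0% to 10% and active rates of 40% to 60%, year-1 power with 15 per arm runs from 0.51 to above 0.99. The sample size may therefore be adequate, but the documents do not show it. The contradiction itself rests on no assumption; only the power figures do, through the assumed rates, the two-sided 0.05 level and the literal t-test. It must be corrected because it is the only sample-size justification in the protocol.

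**What to change.** Rewrite the sample-size paragraph in section 7c so that it agrees with the rest of that section and with sections 4 and 8a.v:

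1. Tie the sizing to a placebo-controlled comparison that will be made, most directly the proportion tolerating 4 g baked milk at DBPCFC #2.
2. State placebo and active rates for that outcome and justify them, saying how the unheated-milk studies, the 444 mg entry criterion and the 21% from the prior baked-milk study were weighed.
3. Give the power of 15 per arm, and of the 14 expected to be evaluable, over a range of rates as in the table above, naming the test and the sidedness.
4. State that the year-2 comparison on 2 g unheated milk is between about 2 years and about 1 year of active OIT, is not placebo-controlled, and is not covered by the stated power.

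The cost is one reworded paragraph. The number of participants, visits and procedures do not change. The only drawback is that the stated power may become less favourable.
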